#### **8.2.6 Vulnerability Elders Survey-13**

The VES-13 will be used to assess frailty in patients with cancer (see [Appendix G](#)). The survey consists of 13 items: 1 item for age and 12 items that assess health, functional capacity, and physical performance ([Saliba et al 2000](#), [Saliba et al 2001](#)). Refer to Section [8.1.4.4](#) for administration details.

### **8.3 Collection of adverse events**

The Investigator is responsible for ensuring that all staff involved in the study are familiar with the content of this section.

The definitions of an AE or SAE can be found in [Appendix B](#).

AE will be reported by the patient (or, when appropriate, by a caregiver, surrogate, or the patient's legally authorized representative).

The Investigator and any designees are responsible for detecting, documenting, and recording events that meet the definition of an AE or SAE. For information on how to follow up AEs, see Section [8.3.3](#).

#### **8.3.1 Method of detecting AEs and SAEs**

Care will be taken not to introduce bias when detecting AEs and/or SAEs. Open-ended and non-leading verbal questioning of the patient is the preferred method to inquire about AE occurrences.

#### **8.3.2 Time period and frequency for collecting AE and SAE information**

AEs and SAEs will be collected from the time of the patient signing the informed consent form until the follow-up period is completed (90 days after the last dose of the IP) (see [Table 1](#) and [Table 2](#)). If an event that starts post the defined safety follow-up period noted above is considered to be due to a late-onset toxicity to study drug, then it should be reported as an AE or SAE, as applicable.

All SAEs will be recorded and reported to the Sponsor or designee within 24 hours, as indicated in [Appendix B](#). The Investigator will submit any updated SAE data to the Sponsor within 24 hours of it being available.

Investigators are not obligated to actively seek AEs or SAEs in former study patients. However, if the Investigator learns of any SAE, including a death, at any time after a patient's last visit and he/she considers the event to be reasonably related to the study treatment or study participation, the Investigator may notify the Sponsor.

The method of recording, evaluating, and assessing causality of AE and SAE and the procedures for completing and transmitting SAE reports are provided in [Appendix B](#).

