**Table 11 Urinalysis**

Bilirubin	Ketones
Blood	pH
Color and appearance	Protein
Glucose	Specific gravity

Note: Microscopy should be used as appropriate to investigate white blood cells and use the high power field for red blood cells. Urinalysis should be done at baseline (screening) and then as clinically indicated.

If a patient shows an AST or ALT  $\geq 3 \times$  ULN together with TBL  $\geq 2 \times$  ULN, refer to [Appendix E](#) for further instructions on cases of increases in liver biochemistry and evaluation of Hy's law. These cases should be reported as SAEs if, after evaluation, they meet the criteria for a Hy's law case or if any of the individual liver test parameters fulfill any of the SAE criteria.

All patients should have further hematology and chemistry profiles performed at 30 days ( $\pm 3$  days), 2 months ( $\pm 1$  week), and 3 months ( $\pm 1$  week) after permanent discontinuation of the IP (see [Table 2](#)).

Any clinically significant abnormal laboratory values should be repeated as clinically indicated and recorded on the eCRF. Situations in which laboratory safety results should be reported as AEs are described in Section [8.3.7](#).

All patients with Grade 3 or 4 laboratory values at the time of completion or discontinuation from the IP must have further tests performed until the laboratory values have returned to Grade 1 or 2, unless these values are not likely to improve because of the underlying disease.

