### **8.3.3 Follow-up of AEs and SAEs**

During the course of the study, all AEs and SAEs should be proactively followed up for each patient for as long as the event is ongoing. Every effort should be made to obtain a resolution for all events, even if the events continue after the patient has discontinued study treatment or the study has completed.

Any AEs that are unresolved at the patient's last visit in the study are followed up by the Investigator for as long as medically indicated but without further recording in the eCRF. AstraZeneca retains the right to request additional information for any patient with ongoing AE(s)/SAE(s) at the end of the study, if judged necessary.

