### **8.3.10 New cancers**

The development of a new cancer should be regarded as an SAE. New primary cancers are those that are not the primary reason for the administration of the IP and have been identified after the patient's inclusion in this study.

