### **8.3.11 Deaths**

All deaths that occur during the study treatment period or within the protocol-defined follow-up period after the administration of the last dose of the IP must be reported as follows:

- Death clearly the result of disease progression should be reported to the Study Monitor/Physician at the next monitoring visit and should be documented in the eCRF in the Statement of Death page. It should not be reported as an SAE.
- Where death is not due (or not clearly due) to progression of the disease under study, the AE causing the death must be reported to the Study Monitor/Physician as an SAE within 24 hours. It should also be documented in the Statement of Death page in the eCRF. The report should contain a comment regarding the co-involvement of PD, if appropriate, and should assign main and contributory causes of death.
- Deaths with an unknown cause should always be reported as an SAE. It should also be documented in the Statement of Death page in the eCRF. A post mortem may be helpful in the assessment of the cause of death, and if performed, a copy of the post mortem results should be forwarded to AstraZeneca Patient Safety or its representative within the usual timeframes.

Deaths occurring after the protocol-defined safety follow-up period after the administration of the last dose of the IP should be documented in the Statement of Death page. If the death occurred as a result of an event that started after the defined safety follow-up period and the event is considered to be due to a late onset toxicity to the IP, then it should also be reported as an SAE.

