Further information on these risks (eg, presenting symptoms) can be found in the current version of the durvalumab IB. More specific guidelines for their evaluation and treatment are described in detail in the Dosing Modification and Toxicity Management Guidelines (see Section 8.4.5.1). These guidelines have been prepared by the Sponsor to assist the Investigator in the exercise of his/her clinical judgment in treating these types of toxicities. These guidelines apply to AEs considered causally related to the study drug/study regimen by the reporting Investigator.

**8.3.13.2 Any event of AESI should be reported to AstraZeneca Patient Safety, whether it is considered a non-serious AE or SAE and regardless of the Investigator's assessment of causality. These AEs must be reported according to the timelines for reporting an SAE to allow for timely safety monitoring. Adverse events of special interest for olaparib**

AESIs for olaparib comprise the important identified risk of MDS/AML and the important potential risks of:

- new primary malignancy (other than MDS/AML)
- pneumonitis

Any event of MDS/AML, new primary malignancy, or pneumonitis should be reported to AstraZeneca Patient Safety whether it is considered a non-serious AE (eg, non-melanoma skin cancer) or SAE, and regardless of Investigator's assessment of causality. These AEs must be reported according to the timelines for reporting an SAE (see Section 8.4.1) to allow timely safety monitoring.

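### From 90 days after last dose until the final data cutoff, the protocol leaves unclear whether MDS/AML and new primary malignancies are reported regardless of causality, and no scheduled contact after Month 3 is stated to ask about them

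*Protocol*

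**What the plan says.** **General window.** Section 8.3.2 collects AEs and SAEs from consent to 90 days after the last dose. An event starting later is reportable if it "is considered to be due to a late-onset toxicity to study drug, then it should be reported as an AE or SAE". The section adds that investigators need not actively look for events in former study patients and may notify the sponsor of an SAE they consider related. Section 8.3.11 applies a similar condition to a death caused by an event that began after the window: if "the event is considered to be due to a late onset toxicity to the IP, then it should also be reported as an SAE".

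**Rule for the named events.** Section 8.3.13.2 states: "AESIs for olaparib comprise the important identified risk of MDS/AML and the important potential risks of" new primary malignancy and pneumonitis. It continues: "Any event of MDS/AML, new primary malignancy, or pneumonitis should be reported to AstraZeneca Patient Safety", serious or not and whatever the causality assessment. The timing reference is to Section 8.4.1, which sets the 24-hour reporting speed. Section 8.3.10 adds: "The development of a new cancer should be regarded as an SAE", for cancers identified after inclusion. Section 8.3.10 has no causality wording of its own; Section 8.4.1 supplies it by requiring all SAEs to be reported whether or not related.

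**After the final data cutoff.** Sections 4.4.1 and 8.3.12 limit SAE reporting to patients on treatment or within 90 days of the last dose.

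**Follow-up schedule.** Table 2 marks AE/SAE assessment and hematology at Day 30, Month 2 and Month 3 only. Section 8.2.1 agrees: "All patients should have further hematology and chemistry profiles performed at 30 days", 2 months and 3 months. Survival status is then checked at Months 4, 6, 8, 10 and 12 and every 2 months thereafter. Those contacts also record subsequent treatment for urothelial cancer.

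**The concern.** Take a patient whose MDS is diagnosed 6 months after the last dose, before the final data cutoff. Under 8.3.13.2 the site reports it without weighing causality. Under 8.3.2 the site reports it if it is judged a late-onset toxicity. Both readings are reasonable, and two sites could treat the same case differently. For a second cancer judged unrelated, the two readings give opposite answers.

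Reporting also depends on the site hearing of the case. After Month 3 the patient is still contacted every 2 months, but no contact is stated to include a question about blood disorders or new cancers.

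What is at stake is consistent capture of a named identified risk of the experimental drug, by randomized arm. PFS and OS are not affected.

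**Working it through.** The plan gives no figure on this point. The check is a comparison of text, followed by an illustration of how long the unclear period lasts.

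**1. Which rule applies, by period**

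| Period | 8.3.2 / 8.3.11 | 8.3.13.2 and 8.4.1 | Clear? |
|---|---|---|---|
| Up to 90 days after last dose | collect | report regardless of causality | yes |
| Day 90 to final data cutoff | report if judged late-onset toxicity | report regardless of causality, no end date | no |
| After final data cutoff | 4.4.1 and 8.3.12 limit SAEs to patients on treatment or within 90 days of last dose | same limit | yes |

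The open interval is the middle row only.

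**2. What already covers part of that row**

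- Events that have already started. Section 8.3.3: "all AEs and SAEs should be proactively followed up for each patient for as long as the event is ongoing".
- Grade 3 or 4 laboratory values present when treatment stops. Section 8.2.1: such patients "must have further tests performed until the laboratory values have returned to Grade 1 or 2", unless improvement is unlikely because of the underlying disease.
- Deaths, which go on the Statement of Death page (8.3.11).
- Patients without progression, who keep having scans (7.1.1).

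None of these is aimed at disease that is new after Day 90, is not fatal, and arises in a patient who has already progressed.

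**3. Count of contacts**

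Post-dose timepoints to Month 24 are Day 30 and Months 2, 3, 4, 6, 8, 10, 12, 14, 16, 18, 20, 22 and 24, which makes 14. AE/SAE assessment is marked at 3 of them, and 14 − 3 = 11 carry none.

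**4. Length of the open interval for the last-recruited patient**

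Final OS cutoff is about 27 months after last recruitment (9.2). Interval = 27 − (months on treatment + 3).

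- Treatment stops at 3 months (planned control median PFS): 27 − 6 = 21 months.
- Stops at 1 month: 27 − 4 = 23 months.
- Stops at 12 months: 27 − 15 = 12 months.

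**5. Share of follow-up time outside the window**

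Inputs from 9.2: PFS median 3 months with HR 0.55, so 3/0.55 = 5.45 months in the combination arm; OS median 16 months with HR 0.75, so 16/0.75 = 21.33 months; 6-month accrual; cutoffs 7 and 27 months after the last patient, that is, months 13 and 33.

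Assumptions: exponential times, uniform entry, death hazard = ln 2 / OS median, progression hazard = ln 2 / PFS median − death hazard, and dosing stops at the PFS event. Time outside = max(0, follow-up − last dose − 3 months). A rerun by simulation (3,000,000 patients per arm) reproduced the values to within 0.001.

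| Scenario | Month 13: control, combination | Month 33: control, combination |
|---|---|---|
| Dosing stops at PFS event | 28%, 18% | 61%, 49% |
| Up to 2 more months of dosing | 16%, 10% | 52%, 42% |
| Combination arm, 9-month median to last dose | –, 9% | –, 31% |

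In the first scenario, survival contacts from Month 4 to month 33 average 5.1 (control) and 4.7 (combination) per randomized patient. With 2 more months of dosing they average 4.4 and 4.1.

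**The case against.** The strongest defence is that there is no contradiction. Section 8.3.2 is the section on time periods, and the others say what is reportable within the period it sets. Section 8.4.1 also has no end date, so on a literal reading every SAE would conflict with 8.3.2. The 90-day limit recurs in 4.4.1, 8.3.12, Table 2 and 9.4.1.2, and passive late collection looks deliberate. This stands in part: the text is an unresolved ambiguity, not a flat contradiction. What remains is that 8.3.13.2 singles these events out, refers only to 8.4.1, and is nowhere made subject to the 90-day limit before the final cutoff.

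A second defence is that a late MDS/AML case known to the site already has a route, because an identified risk is readily judged a late-onset toxicity. That also has force. It helps less for a new primary cancer judged unrelated, and not at all for a case the site never hears of. Section 7.1.1 asks for continued visits or a modified follow-up that gathers safety information, but Table 2 schedules no AE question after Month 3.

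A reader might infer three stronger points that the documents do not support:

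- *The person-time shares measure missed cases.* They do not. They run from 9% to 61% depending on arm, cutoff and treatment duration, and the larger control-arm values concern patients not given olaparib.
- *Late events drop out of the report.* Section 9.4.1.2 leaves them out of the AE summary tables but requires a separate listing of AEs beyond 90 days.
- *The older wording on causality in 2.3.3.2 makes the plan wrong here.* That is background text which defers to the current Investigator's Brochure.

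**Conclusion.** The point holds as an ambiguity combined with a detection gap, confined to the interval from 90 days after last dose to the final data cutoff. In that interval it is unclear whether MDS/AML and new primary malignancies are reported regardless of causality or only if judged late-onset toxicity. New-onset, non-fatal cases, mainly in progressed patients, may be missed or handled differently between sites.

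The interval is long relative to the trial: 12 to 23 months for a last-recruited patient who stops treatment between months 1 and 12. The number of affected cases cannot be derived, because the protocol gives neither an incidence nor a latency. The PFS and OS analyses are untouched. This is a modest, worthwhile clarification of safety reporting.

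**What to change.** Add to Section 8.3.2, with a matching row in Table 2:

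*Until the final DCO, MDS/AML and new primary malignancies are asked about at each scheduled 2-monthly survival contact and reported regardless of causality; for these events this overrides the 90-day limit and the late-onset-toxicity condition in 8.3.2 and 8.3.11.*

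The cost is one question at a contact that already takes place and one sentence of precedence, with no new visit or blood sample. The drawback is that some late cases may be due to subsequent anticancer therapy; that therapy is already recorded, so those cases can be flagged. Late cases would appear in the listing of AEs beyond 90 days already planned in 9.4.1.2, so no further table is needed.

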### **8.3.3 Follow-up of AEs and SAEs**

During the course of the study, all AEs and SAEs should be proactively followed up for each patient for as long as the event is ongoing. Every effort should be made to obtain a resolution for all events, even if the events continue after the patient has discontinued study treatment or the study has completed.

Any AEs that are unresolved at the patient's last visit in the study are followed up by the Investigator for as long as medically indicated but without further recording in the eCRF. AstraZeneca retains the right to request additional information for any patient with ongoing AE(s)/SAE(s) at the end of the study, if judged necessary.

### **8.3.4 Adverse event data collection**

The following variables will be collected for each AE:

- AE (verbatim)
- The date when the AE started and stopped
- The maximum CTCAE grade reported
- Changes in CTCAE grade (report only the maximum CTCAE grade for a calendar day)
- Whether the AE is serious or not
- Investigator causality rating against the IPs (yes or no)
- Action taken with regard to the IPs
- Administration of treatment for the AE
- Outcome

In addition, the following variables will be collected for SAEs:

- Date AE met criteria for SAE
- Date Investigator became aware of SAE
- Seriousness criteria

- Date of hospitalization
- Date of discharge
- Probable cause of death
- Date of death
- Whether an autopsy was performed
- Causality assessment in relation to study procedure(s)
- Causality assessment in relation to other medication, as explained in Section 8.3.5
- Description of the SAE

The grading scales found in the revised NCI CTCAE version 4.03 will be utilized for all events with an assigned CTCAE grading. For those events without assigned CTCAE grades, the recommendation in the CTCAE criteria that converts mild, moderate, and severe events into CTCAE grades should be used. A copy of the CTCAE version 4.03 can be downloaded from the Cancer Therapy Evaluation Program website (<http://ctep.cancer.gov>).

It is important to distinguish between serious and severe AEs. Severity is a measure of intensity, whereas seriousness is defined by the criteria in [Appendix B, B 2](#). An AE of severe intensity need not necessarily be considered serious. For example, nausea that persists for several hours may be considered severe nausea, but not an SAE unless it meets the criteria shown in [Appendix B, B 2](#). On the other hand, a stroke that results in only a limited degree of disability may be considered a mild stroke, but it would be an SAE if it satisfies the criteria shown in [Appendix B, B 2](#).

### **8.3.5 Causality collection**

The Investigator will assess causal relationship between the IP and each AE, and answer “yes” or “no” to the question “Do you consider that there is a reasonable possibility that the event may have been caused by the IP?”

For SAEs, causal relationship will also be assessed for other medication and study procedures. Note that for SAEs that could be associated with any study procedure, the causal relationship is implied as “yes.”

A guide to the interpretation of the causality question is found in [Appendix B](#).

### **8.3.6 Adverse events based on signs and symptoms**

All AEs spontaneously reported by the patient or reported in response to the open question from the study site staff, “Have you had any health problems since the previous visit/you were last asked?”, or revealed by observation will be collected and recorded in the eCRF. When collecting AEs, the recording of diagnoses is preferred (when possible) to recording a list of signs and symptoms. However, if a diagnosis is known and there are other signs or symptoms that are not generally part of the diagnosis, the diagnosis and each sign or symptom will be recorded separately.

### **8.3.7 Adverse events based on examinations and tests**

The results from the protocol-mandated laboratory tests and vital signs will be summarized in the clinical study report (CSR). Deterioration as compared to baseline in protocol-mandated laboratory values, and vital signs should therefore only be reported as AEs if they fulfil any of the SAE criteria or are the reason for discontinuation of treatment with an IP.

If deterioration in a laboratory value/vital sign is associated with clinical signs and symptoms, the sign or symptom will be reported as an AE, and the associated laboratory result/vital sign will be considered as additional information. Wherever possible, the reporting Investigator uses the clinical rather than the laboratory term (eg, anemia versus low hemoglobin value). In the absence of clinical signs or symptoms, clinically relevant deteriorations in non-mandated parameters should be reported as AEs.

Deterioration of a laboratory value that is unequivocally due to disease progression should not be reported as an AE/SAE.

Any new or aggravated clinically relevant abnormal medical finding at a physical examination as compared with the baseline assessment will be reported as an AE.

### **8.3.8 Hy’s law**

Cases where a patient shows elevations in liver biochemistry may require further evaluation, and occurrences of AST or ALT  $\geq 3 \times$  ULN together with TBL  $\geq 2 \times$  ULN may need to be reported as SAEs. Please refer to [Appendix E](#) for further instruction on cases of increases in liver biochemistry and evaluation of Hy’s law.

### **8.3.9 Disease progression**

Disease progression can be considered as a worsening of a patient's condition attributable to the disease for which the IP is being studied. It may be an increase in the severity of the disease under study and/or increases in the symptoms of the disease. The development of new or progression of existing metastasis to the primary cancer under study should be considered as disease progression and not an AE. Events that are unequivocally due to disease progression should not be reported as an AE during the study.

### **8.3.10 New cancers**

The development of a new cancer should be regarded as an SAE. New primary cancers are those that are not the primary reason for the administration of the IP and have been identified after the patient's inclusion in this study.

### **8.3.11 Deaths**

All deaths that occur during the study treatment period or within the protocol-defined follow-up period after the administration of the last dose of the IP must be reported as follows:

- Death clearly the result of disease progression should be reported to the Study Monitor/Physician at the next monitoring visit and should be documented in the eCRF in the Statement of Death page. It should not be reported as an SAE.
- Where death is not due (or not clearly due) to progression of the disease under study, the AE causing the death must be reported to the Study Monitor/Physician as an SAE within 24 hours. It should also be documented in the Statement of Death page in the eCRF. The report should contain a comment regarding the co-involvement of PD, if appropriate, and should assign main and contributory causes of death.
- Deaths with an unknown cause should always be reported as an SAE. It should also be documented in the Statement of Death page in the eCRF. A post mortem may be helpful in the assessment of the cause of death, and if performed, a copy of the post mortem results should be forwarded to AstraZeneca Patient Safety or its representative within the usual timeframes.

Deaths occurring after the protocol-defined safety follow-up period after the administration of the last dose of the IP should be documented in the Statement of Death page. If the death occurred as a result of an event that started after the defined safety follow-up period and the event is considered to be due to a late onset toxicity to the IP, then it should also be reported as an SAE.

